The rationale for the duration of the interventions, follow up, and blinding procedures: The proposed study is of standard duration for the geriatric population requiring 12 weeks or longer trials to document antidepressant efficacy.

4.0 *Research Design and Methods: Describe in detail the design and methodology of the study.

Subjects: We anticipate screening about 100 subjects to recruit 60 older depressed adults (>60 y.o.) who will be randomized to receive 20-120 mg of levomilnacipran blindly with increment dose titration 20 mg per day -3 days; 40 mg per day-3 days. Based on efficacy and tolerability, we will increase by 40 mg per day each following week 2nd-4th week the maximum recommended doses is 120 mg per day. The comparison group will receive similar blinded titration with matching placebo. Doses of the drugs will be adjusted according to individual tolerability and safety. We expect an attrition rate of about 10% based on our prior experience thus 54 subjects will complete the study. Patients will be assessed pre-treatment; and then weekly during the first four weeks and bi-weekly thereafter. At all visits, clinical ratings of mood, vital signs, and safety will be obtained. Inclusion criteria: 1) The presence of a major depressive disorder diagnosed according to the DSM-IV criteria. 2) A 24-item Hamilton Rating Scale for Depression (HAMD) score of 17 or higher at baseline. 3) Mini-Mental State Exam (MMSE) score > 24.

Exclusion criteria: subjects will be excluded if they had 1) any current and/or lifetime history of other psychiatric disorders (except unipolar depression with or without comorbid generalized anxiety disorder), or 2) recent unstable medical or neurological disorders; 3) any disabilities preventing their participation in the study or in the MRI; 4) diagnosis of dementia; 5) acute suicidality; 6) those with known allergic reactions to milnacipran, uncontrolled narrow angle glaucoma, seizures, poorly-controlled hypertension or ischemic changes on ECG, serotonin syndrome, or the recently used MAOIs within last 4 weeks; 7) ineligible for MRI (e.g., metal in the body or claustrophobia)

Primary outcome will be measured and defined as follows: 1) Remission will be defined as HAMD scores of 6 or less for three consecutive weeks and at week 12; 2) Improvement in depression severity using HAMD scores.

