Imaging Biomarkers: Imaging data will be acquired from each subject at baseline and at 12-weeks post-randomization on a Siemens 3T Trio system using a 32-channel head coil. Each scanning session will last 60 minutes and include 1) a T1-weighted multi-echo MPRAGE (MEMPR) sequence with real time motion correction53 for the examination of brain structure and for use in network analyses; 2) a matched bandwidth T2 sequence for the detection and quantification of WMHs and CSF; 3) rs-fMRI to examine treatment related changes in functional activity at rest and intrinsic network connectivity; and 4) high angular resolution diffusion imaging (HARDI) to isolate changes in white matter microstructure and structural connectivity. Both rs-fMRI and diffusion imaging will utilize recently developed accelerated multiband pulse sequences with optimized spatial and temporal resolution (Table 3).54,55 Notably, the same multimodal imaging protocol has been implemented for a NIH study addressing biomarkers of geriatric depression in association with escitalopram both with and without augmentation of memantine treatment. In a separate extramurally funded project, we are also using this protocol to examine treatment effects and brain aging associated with Kundalini yoga. We are thus able to pool data and/or contrast results across studies as might be appropriate.

Resting State fMRI: During acquisition of blood-oxygen-level-dependent (BOLD) rs-fMRI data, subjects will remain awake with their eyes closed. Preprocessing will occur in a parallelized supercomputing environment using FSL56-58 and custom processing modules. Independent components analysis (ICA),59,60 will estimate the optimal number of components for each subject and time point and identify components representing artifacts. After low pass filtering (0.1-0.01 Hz) and transformation into atlas space, the best-fit default mode network (DMN) and executive and memory function network will be selected for each subject/time point for higher-level analysis. In follow-up analyses, seed regions-of-interest (ROIs) will be employed to examine voxel-level correlations between particular network nodes.60-62 In addition to subtracting changes between baseline and follow-

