Hypothesis 1: The primary analyses will focus upon HAM-D24 scores and will be analyzed using general linear mixed model analysis (e.g., SAS PROC MIXED). The two treatment groups will be compared for time course of HAM-D-24 with the initial endpoint EOT at 12 weeks. Covariates may be included in the model as noted above. In addition, likelihood ratio ?2 comparison will examine group differences in remission (HAM-D24 =6) and response (HAM-D24 =10) at EOT. Analyses for the cognitive outcome variables will be akin to those described above for the continuous HAM-D scores. As noted in the Neuropsychological Assessment section, there are four cognitive domains that are being assessed. Of these, the two primary cognitive domains of interest for this proposal are Cognitive Control and Episodic Memory. A separate general linear mixed model as above will be estimated using these two domain scores as dependent variables. The remaining domains, namely Verbal Fluency and Information Processing/Attention will be examined as secondary outcome measures. Apathy will be examined using the AES total score and quality of life using SF-36 scores in similar mixed models.

Hypothesis 2: We will examine adverse events in the two treatment groups. A detailed comparison of the number as well as type of side-effects in the two treatment groups will be conducted using chi-square tests.

Hypothesis 3: LMIL will lead to improved functional connectivity in brain network activity as measured with resting state (rs-) fMRI, and plasticity in brain macro- and micro-structure as measured with structural MRI and DTI compared to the PBO. To address these hypothesis, summary MRI measures (e.g., substructure volume, diffusion metrics) will be included in the GLMMs as "covariates of interest." For whole brain or structure voxel-level or point based measures (e.g., thickness or activation), the GLMMs will be implemented in R (www. R.org). Time (of scan) will be treated as a continuous variable with random intercepts and slopes to account for within-subject correlations between repeated measurements to assess change and interactions amongst the interventions. Difference scores between baseline and 12-week follow-up may be substituted for some analyses. FDR and/or permutation methods will be used to control for multiple anatomic comparisons in whole-brain contexts.

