Hypothesis 4: The role of brain neuroimaging biomarkers in variability of treatment response is examined in this Hypothesis. Predictor variables: We predict that baseline measures of neuroimaging biomarkers of emotional responsivity; working memory and connectivity will be related to treatment outcomes. These predictions will be evaluated in the context of the models described above (i.e., general linear mixed model) by adding the posited prognostic variable as an additional predictor.

Power. With a significance level (alpha) of 0.05, 80% power, and N = 30 in each treatment arm, we can detect an effect size (ES, difference between group means as a multiple of the standard deviation) of 0.7. Using appropriate covariates such as age of onset, chronicity, and number of episodes can be expected to reduce variance and increase power for a given difference in mean, hence the two-sample power computations are conservative for this situation. This study will thus yield sufficient pilot data to justify conducting a larger study in the future.

Data management. Data management and analysis support will be provided by the UCLA SI-STAT services and [name] will supervise the data gathering duties of the study coordinator, including reviewing all data entry forms. 1. Randomization. The prestudy forms must be submitted before a patient can be randomized. A separate portion of the database will also be maintained for patients screened but not enrolled or randomized. Randomization schedules will be prepared in a masked manner by the statistician. 2. Data submission and quality control. Data forms will be delivered from the originating location to the central data unit within one week of being generated. When errors, omissions, or unclear information is detected on the paper forms, a copy

will be returned for corrections. The data manager will generate monthly reports summarizing missing and incorrect data will be sent to the PI. 3. Data confidentiality. Patient study forms will be stored in locked file cabinets and will be accessible only to authorized personnel. A shredder will be used to discard all unwanted study documents. Access to the data will be password protected with only authorized persons having knowledge of the password.

ID: IRB#14-001827

View: NEW 11.1 - Characteristics of the Study Population

Warning: Save your work at least every 15 minutes by clicking \$Save\$ or \$Continue.

Characteristics of the Study Population

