- If you selected Cash and/or Gift Cards/Bruincard Deposit please specify the estimated total amount of money you will require to pay all participants during the length of the entire study. This information is required by UCLA Business and Finance Services (BFS), the office that will provide the cash/gift cards for payment.
- 2.0 If study participants will receive financial or other payment for their participation in the study, please provide the following information:
 - If applicable, the amount each participant will receive and the payment schedule to be followed including whether partial payment will be provided when the participant does not complete the study.
 - If there are different plans for different populations or sub-studies, specify the groups and describe the plans.
 - If families or children will be involved in the research, clarify how the payments, items or services will be

	apportioned.
	The subjects will receive a \$100.00 honorarium for their participation in the 12 week trial (\$10 per visit), and \$50.00 per MRI scan (\$100.00) for a total up to \$200.
3.0	Will subjects incur any financial obligations from participation in the study? ○ Yes ● No
	 3.1 If yes, describe:
4.0	Indicate below that you are familiar with UCLA policy related to treatment and compensation for injury and that you will use not the consent form for this study the appropriate UC required statement describing "Treatment and Compensation for nijury." Click here to access the UCLA policy: Treatment and Compensation for Research Related Injury.
4.0	n the consent form for this study the appropriate UC required statement describing "Treatment and Compensation for njury." Click here to access the UCLA policy: Treatment and Compensation for Research Related Injury. Note: Select Not Applicable if study is minimal risk.
4.0	n the consent form for this study the appropriate UC required statement describing "Treatment and Compensation for njury." Click here to access the UCLA policy: Treatment and Compensation for Research Related Injury. Note: Select Not Applicable if study is minimal risk. Agree
4.0	n the consent form for this study the appropriate UC required statement describing "Treatment and Compensation for njury." Click here to access the UCLA policy: Treatment and Compensation for Research Related Injury. Note: Select Not Applicable if study is minimal risk.

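### With two scans per participant, the random-slope variance in the Hypothesis 3 imaging model cannot be separated from scan noise; an identified two-occasion model should be named instead

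*Combined protocol and SAP*

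**What the plan says.** The Hypothesis 3 paragraph of Section 10.1, item 6.0, sets out mixed models for the imaging measures and specifies: "Time (of scan) will be treated as a continuous variable with random intercepts and slopes to account for within-subject correlations between repeated measurements". The purpose given is to assess change and its interaction with the interventions. For voxel-level or point-based measures, "the GLMMs will be implemented in R". The next sentence adds an alternative: "Difference scores between baseline and 12-week follow-up may be substituted for some analyses". It does not say which analyses or what would trigger the switch. The covariance structure of the random effects is not stated.

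The schedule is in Section 10.1, item 4.0, Imaging Biomarkers: "Imaging data will be acquired from each subject at baseline and at 12-weeks post-randomization". Section 16.1, item 2.0, agrees with it: $50 per scan and $100 in total, so two scans. No third scan, repeat scan at one visit, or scan-date window is given. On retention, item 4.0 says: "We expect an attrition rate of about 10% based on our prior experience thus 54 subjects will complete the study".

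**The concern.** A random slope describes how participants differ in their own rate of change. To separate that from scan-to-scan noise, the data must show how far each person's values scatter around that person's own line. Two points always lie exactly on a line, so two scans leave no such scatter.

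If the sentence is applied as written, the reported slope variance and residual variance are whatever split the optimiser stops at, and the subject-specific slopes inherit that choice. Fits may be singular, fail or be refused. When the model is run at every voxel, this can vary across the brain. With difference scores left optional, the method could then be chosen measure by measure after some fits have failed. The Power paragraph of item 6.0 says that the study is meant to yield pilot data for a larger trial, and variance components from this model would be a poor basis for planning one.

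**Working it through.** **Inputs.** Two scans per participant (item 4.0 and the payment in Section 16.1). 60 randomised and 54 expected to complete (item 4.0). Random intercepts and slopes over continuous time (item 6.0). All variance values and date spreads below are assumptions, since the documents give none.

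**1. Parameter count.** Take 12 weeks as one time unit. Let a be the intercept variance, c the intercept-slope covariance, b the slope variance and s the residual variance.

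- Baseline variance = a + s
- Covariance of the two scans = a + c
- Week-12 variance = a + 2c + b + s

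There are three equations and four unknowns. The Jacobian has rank 3. Changing (a, c, b, s) by (−1, +1, −2, +1) leaves all three moments unchanged.

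**2. Example.** Let both variances be 1 and the covariance 0.7. These four sets fit identically:

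| s | a | c | b |
|---|---|---|---|
| 0 | 1.0 | −0.3 | 0.6 |
| 0.1 | 0.9 | −0.2 | 0.4 |
| 0.2 | 0.8 | −0.1 | 0.2 |
| 0.3 | 0.7 | 0 | 0 |

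The data cannot tell a slope variance of 0.6 from one of zero.

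**3. One simulated trial** (30 per arm, no dropout, true effect 0.30). Three optimisers reached the same log-likelihood, −153.75071:

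| Fit | s | b | b + 2s |
|---|---|---|---|
| 1 | 0.2197 | 0.0208 | 0.4602 |
| 2 | 0.1608 | 0.1386 | 0.4602 |
| 3 | 0.2213 | 0.0175 | 0.4601 |

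The slope variance differs about eightfold (0.1386 / 0.0175), while b + 2s, which is constant along the direction in step 1, does not move. The group-by-time estimate was 0.5237 with standard error 0.1751 in all three. A t-test on difference scores gave the same estimate (t = 2.99), and a random-intercept model gave the same estimate and standard error.

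**4. Number of random effects.** 60 × 2 = 120, against at most 120 scans, or 60 + 54 = 114 if all six dropouts miss week 12. A program that requires more observations than random effects would refuse the model.

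**5. Uncorrelated intercept and slope.** With c = 0 there are three parameters for three moments, so the model is identified. Then b = week-12 variance − baseline variance. Its estimate falls on the boundary at zero whenever the observed week-12 variance is the smaller. In a simulation of 54 pairs this happened in 49% of data sets when the true variances were equal, and in 31% with true b = 0.1 and s = 0.3.

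**6. Scatter in scan dates.** Expected Fisher information with 54 pairs, 6 baseline-only scans, uniform scatter in the week-12 date, and assumed a = 0.8, c = −0.05, b = 0.1, s = 0.2:

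| Spread | SE(b), true 0.1 | SE(s), true 0.2 |
|---|---|---|
| ±0.5 week | 1.96 | 0.98 |
| ±1 week | 0.99 | 0.49 |
| ±2 weeks | 0.48 | 0.25 |
| ±4 weeks | 0.26 | 0.13 |

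With a = 0.6, c = 0, b = 0.1, s = 0.3 and 54 pairs, SE(b) is about 3.2 at ±3 days and 1.34 at ±7 days. Even ±4 weeks leaves the standard error of b at more than twice its assumed value.

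**7. Precision of the preferred alternative.** With equal variances σ² and scan-to-scan correlation r, the change score has variance 2σ²(1 − r) and the baseline-adjusted week-12 value has σ²(1 − r²). The ratio is (1 + r)/2: 0.75 at an assumed r of 0.5 and 0.95 at 0.9.

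**The case against.** The strongest reply is that Hypothesis 3 concerns the difference in change between groups, and that this contrast is unharmed. With two common times, random intercept, slope and residual span the same covariance matrices as an unstructured 2 × 2 model, so the treatment-by-time estimate and standard error are the same. This stands, and step 3 shows it. In a further simulation of 60 data sets with six baseline-only participants, all 180 fits (three optimisers each) reported convergence. In 59 of the 60, the group-by-time z statistic agreed to within 0.01 across optimisers; in the other, one optimiser returned no usable standard error. Failed fits are thus a risk and not a certainty.

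Second, the plan does not say that intercept and slope are correlated, and scan time is continuous. Both points are correct. But the uncorrelated form is identified only by that assumption, with the boundary problem in step 5, and date variation adds little (step 6).

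Third, change-based methods already appear. The Structural Imaging paragraph of item 4.0 describes tensor-based morphometry (TBM) that warps baseline to follow-up scans, with general linear models. The Resting State fMRI paragraph subtracts baseline from follow-up for associations with clinical response. Item 6.0 enters summary MRI measures in the mixed models as covariates. A reader might infer that the random-slope model is the default for every imaging measure; these passages do not support that. The point is confined to uses of that mixed model with an imaging measure as the outcome, for which no identified method is named as the main one.

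**Conclusion.** The point holds in a limited form. The two-scan design cannot support the random-slope variance unless intercept and slope are assumed uncorrelated, and the plan makes no such statement. The variance components and subject-specific slopes would be arbitrary, and singular, failed or refused fits are a practical risk, chiefly in voxel-by-voxel work.

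A reader might go further and infer that the Hypothesis 3 analysis cannot be run, or that the tested brain maps depend on the optimiser. The documents do not support this: the stated purpose is change and its interaction with treatment, that contrast is estimable, and nothing promises a reported slope variance or individual slopes.

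The rank result needs only a common 12-week interval and an unrestricted covariance. The standard errors and boundary frequencies rest on assumed variances and date spreads. Severity is low to moderate: Section 10.1, item 2.0, labels Aim 3 exploratory, and the primary HAM-D analysis is untouched.

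**What to change.** In the Hypothesis 3 paragraph of item 6.0, delete the random slopes and name one main model wherever that mixed model was to be used with an imaging measure as the outcome.

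- Preferred: the week-12 value modelled on treatment plus the baseline value of the same measure (for voxel-level work, the value at that voxel).
- Otherwise: a two-occasion model with treatment, visit and treatment × visit, using either a random intercept only or an unstructured 2 × 2 covariance.

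The chosen model should replace the open-ended option of difference scores. The change-based TBM analyses in the Structural Imaging paragraph can stay as they are.

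The cost is about one sentence of text and simpler code, with no new data. Individual slopes would not be reported, but two scans could not have supported them. The preferred model uses only participants with a week-12 scan, 54 at the expected attrition; the two-occasion model also keeps baseline-only participants.

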Randomization and treatment schedule: After all screening and baseline test results are reviewed and eligibility criteria are confirmed, medications will be dispensed if patients continue to meet eligibility criteria and sign the informed consent form. All eligible subjects will be randomized to levomilnacipran or placebo group using a computer-generated random assignment scheme, which assigned subjects in a 1:1 ratio to each group. Randomization will be done prior to subject s being assigned to the groups.

Follow up assessment: The follow up will take place weekly for the first four weeks of treatment, every two weeks for the remainder of the study. Each follow up assessment will include measures of efficacy and safety. The weekly frequency of contact with all subjects will serve as an additional safeguard to monitor worsening of depression, as well as the emergence of side-effects or suicidal ideations.

Study medications and treatment procedures. Subjects will be randomized to: 1) LMIL20-120 mg per day or 2) matching placebo. The allowed range of the drugs according to tolerability and efficacy assessments will be between 20-120 mg per day for LMILN. The dose finding procedures will be only performed in the first four weeks and after that will remain stable until the end of the acute trial, as it worked in our pilot study. We will assess the optimal dose of LMIL based on tolerability and safety in this population. The balance will be maintained between the efficacy and tolerability of medications. If symptoms worsen, the study drug will be tapered and discontinued. Subjects will be referred for clinical care at UCLA or the community. The PI will continue the observation for safety until the appointment is scheduled with the primary psychiatrist. The dose will be titrated according to the titration schedule, including if side-effects are mild or well tolerated and if CGI scores for improvement is 3 or higher. The titration rate is based on the currently recommended titration to achieve the greatest efficacy that may not work for geriatric patients. For that reason, we have safeguards against rapid titration with potential side-effects that will require a slower titration or staying at a lower dose.

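### For the exploratory drug-placebo comparison of summary imaging measures, neither the stated mixed model nor its difference-score substitute adjusts for the baseline value of the measure

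*Combined protocol and SAP*

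**What the plan says.** Section 10.1 item 4.0 (Imaging Biomarkers) sets two scans per subject: "Imaging data will be acquired from each subject at baseline and at 12-weeks post-randomization".

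The Hypothesis 3 paragraph of item 6.0 gives the default imaging model: "Time (of scan) will be treated as a continuous variable with random intercepts and slopes to account for within-subject correlations between repeated measurements". It then allows a substitute: "Difference scores between baseline and 12-week follow-up may be substituted for some analyses". It does not say which analyses these are.

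No imaging analysis uses the baseline value of the measure as a covariate or constrains the arms to a common baseline mean. The covariates that item 6.0 names are demographic and illness-course variables; the Power paragraph relies on age of onset, chronicity and number of episodes to reduce variance.

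On size, the Subjects paragraph of item 4.0 says: "We expect an attrition rate of about 10% based on our prior experience thus 54 subjects will complete the study". Randomisation "assigned subjects in a 1:1 ratio to each group". The only power statement is general, with no imaging effect size. It takes 30 subjects per arm, alpha 0.05 and 80% power, and concludes: "we can detect an effect size (ES, difference between group means as a multiple of the standard deviation) of 0.7".

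**The concern.** Hypothesis 3 predicts better connectivity and structural plasticity on levomilnacipran than on placebo, so it needs a comparison between randomised arms. The baseline scan is already collected, and in a randomised comparison its main statistical use is to remove between-subject variation from the week-12 value.

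A difference score uses the baseline with its slope fixed at 1. When the true slope is below 1, this over-corrects and carries baseline noise into the estimate. The default mixed model does the same when there are two scans and the arm baselines are free.

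What is at stake is precision, not validity: both estimators are unbiased under randomisation. With about 27 per arm, avoidable noise widens the intervals around the imaging effect estimates that a pilot is meant to supply for a later study.

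**Working it through.** **Inputs.** Two scans per subject (item 4.0, Imaging Biomarkers). 54 completers of 60 (Subjects paragraph), 1:1 allocation, so 54/2 = 27 per arm. The 27 is derived: it assumes equal losses and two usable scans in every completer. Alpha 0.05 and 80% power (Power paragraph); sidedness is not stated, so two-sided is assumed. Rho is not given; 0.3 to 0.95 is assumed.

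**The plan's own figure.** At 30 per arm, two-sided 0.05 and 80% power, the detectable effect is 0.736 SD (noncentral t) or 0.723 SD (normal approximation). Power for 0.7 SD is 76.0% or 77.4%. One-sided testing gives about 0.64 SD, which fits no better. The stated 0.7 is therefore matched only by rounding to one decimal, and nothing below depends on it. At 27 per arm the noncentral t gives 0.777 SD.

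**Step 1: the default and the substitute give the same estimate.** With complete data at two common times and a free mean for each arm at each time, the group-by-time estimate is the difference between arms in mean change. In 150 simulated trials of 54 subjects at each of rho 0.5 and 0.8, a random-intercept model with group, time and their interaction matched the difference score to about 2e-15. A random slope does not alter this. Nor can it be separated from residual error with two scans, because four covariance parameters would have to be estimated from three observable moments (two variances and one covariance).

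**Step 2: variance per subject.** In units of the common variance:

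- difference score: 2(1 - rho)
- baseline-adjusted: 1 - rho^2 = (1 - rho)(1 + rho)
- ratio, adjusted to difference: (1 + rho)/2

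**Step 3: detectable effect at 27 per arm.** Difference score: 0.777 × √(2(1 - rho)), 52 df. Adjusted: essentially 0.777 × √(1 - rho^2), 51 df. At rho 0.5 these are 0.777 × 1.000 = 0.777 and 0.777 × 0.866 = 0.673.

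| rho | Variance saved by adjusting | Detectable SD, adjusted | Detectable SD, difference | Subjects per arm the difference score is worth, 27(1 + rho)/2 | Adjusted power where the difference score has 80% |
|---|---|---|---|---|---|
| 0.3 | 35% | 0.741 | 0.919 | 17.6 | 93.5% |
| 0.5 | 25% | 0.673 | 0.777 | 20.2 | 89.9% |
| 0.7 | 15% | 0.555 | 0.602 | 22.9 | 85.9% |
| 0.9 | 5% | 0.339 | 0.347 | 25.6 | 81.9% |
| 0.95 | 2.5% | 0.243 | 0.246 | 26.3 | 81.0% |

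Below rho 0.5 the difference score is less precise than ignoring the baseline scan: at rho 0.3 its variance is 2 × 0.7 = 1.4, against 1.0 for the week-12 value alone.

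**Step 4: simulation.** SD of the treatment estimate over the 150 trials:

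| rho | Difference score | Mixed model, free baselines | Baseline-adjusted | Mixed model, common baseline |
|---|---|---|---|---|
| 0.5 | 0.263 | 0.263 | 0.217 | 0.215 |
| 0.8 | 0.166 | 0.166 | 0.160 | 0.158 |

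The formulas give √(2/27) × 1.000 = 0.272 and √(2/27) × 0.866 = 0.236 at rho 0.5. At rho 0.8 they give 0.172 and 0.163. With only 150 trials the simulated values scatter around these, but the ordering agrees.

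**Step 5: unequal variances.** If the scan SDs are s0 (baseline) and s1 (week 12), the excess variance of the difference score is (s0 - rho·s1)^2 = s0^2(1 - b)^2, where b = rho·s1/s0 is the slope on baseline. The loss is zero when b = 1, whatever the correlation. The table therefore depends on the equal-variance assumption.

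**The case against.** A reader might infer that the difference-score sentence itself gives away precision. The documents do not support that. The sentence substitutes for a mixed model, not for a baseline-adjusted comparison, and with two complete scans the two give the same answer. The shortfall belongs to the default as much as to the substitute, so changing only the quoted sentence would not cure it.

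A reader might also infer that resting-state connectivity loses most because it repeats poorly. Nothing in the plan says so; the Resting State fMRI paragraph describes resting-state activations as very repeatable. No correlation is given for any modality, so the measures cannot be ranked.

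Other objections stand in part:

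- The wording is permissive. The one use of subtraction that the plan spells out (Resting State fMRI) relates change to clinical response and neuropsychological function. The efficiency argument for randomised arms does not carry over directly to those association analyses.
- Item 6.0 enters summary MRI measures into the models as explanatory terms of interest. That they are outcomes is inferred from the wording of Hypothesis 3.
- The Structural Imaging paragraph uses tensor-based morphometry, whose longitudinal quantity is already a within-subject change, so it has no baseline value of the same kind to adjust for.
- The aim is exploratory, the estimators are unbiased, and at rho 0.9 to 0.95 the gain is slight.

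These limit the scope and the severity. They do not remove the point for two-scan summary measures compared between arms.

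**Conclusion.** The point holds as a low-severity, nearly free improvement. For drug-placebo comparisons of two-scan summary imaging measures, neither analysis the plan describes adjusts for the measure's own baseline.

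The size depends on rho: from 35% of the variance at 0.3 down to 2.5% at 0.95. That is a worthwhile gain for moderately repeatable measures and a negligible one for highly repeatable ones.

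The figures assume randomised arms, equal variances at the two scans, complete pairs at common times, about 27 per arm, two-sided 0.05, and no common-baseline constraint in the mixed model (none is stated). This is not an error that invalidates Hypothesis 3, and it does not bear on the HAM-D24 analysis.

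**What to change.** In the Hypothesis 3 paragraph, for treatment comparisons of summary imaging measures, replace both the random-slope specification and the difference-score sentence with text such as:

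> Levomilnacipran-placebo comparisons of summary imaging measures will use the week-12 value as outcome with the baseline value of the same measure as covariate, or a mixed model in which the arms share a common baseline mean. Analyses that use difference scores are listed in advance.

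Keep change measures for tensor-based morphometry, and for the fMRI change maps and association analyses described under Resting State fMRI. State in the same paragraph that the summary measures are the outcomes of these comparisons.

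The cost is a short rewrite of one paragraph, one degree of freedom for the covariate, and minor extra analysis work. No new scans, visits or subjects are needed.
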